2. Time to failure: To compare time to failure between MUS+BPTx versus MUS alone.
-Failure will be defined as initiation of any additional treatment for lower urinary tract symptoms (SUI, UUI/OAB, or voiding dysfunction).

3. Predictors of poor outcomes: To develop models to identify predictors of change of MUI, OAB, and SUI outcomes measured using the UDI between baseline and 1 year post-treatment.

4. Quality of life and global impression: To compare quality of life outcomes and Patient Global Impression-Improvement (PGI-I)³, Patient Global Impression-Severity (PGI-S)³ between groups

5. Safety and additional treatments: To describe rates of reoperation (sling revision) for worsening OAB symptoms after MUS and to compare the proportion of women in each group initiating additional treatment for SUI and/or OAB, and the types of additional treatment (BPTx, medications, other)

6. Minimally important difference (MID) and clinical definitions: To determine MIDs and clinically meaningful definitions of MUI that predict clinical outcomes using cut-offs and combinations of standardized measures

7. Pelvic floor muscle strengthening: To compare pelvic floor muscle strength changes between women randomized to combined MUS+BPTx versus MUS alone and to estimate associations between pelvic floor muscle strength improvement and UI symptoms. We will also explore predictors of unsuccessful pelvic floor muscle strengthening.

8. Cost-effectiveness analysis: To determine the cost effectiveness of combined midurethral sling (MUS) and peri-operative behavioral/pelvic floor therapy (BPTx) compared to MUS alone for the treatment of MUI symptoms

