9.5.3 Predictors of Treatment Success and Failure

Regression models will be created to identify predictors of change from baseline to 1 year for UDI total score and stress and irritative subscale scores. Participants who request additional treatment prior to 1 year will not be included in the predictive models. Potential predictors will include age, diary parameters such as number of UUI episodes/3 days, functional bladder capacity, bother severity at baseline. The relationship between potential predictors and outcomes will be explored in models that include one predictor plus stratification factors (center and baseline urge IE group). Predictive models will be constructed using backward selection of predictors. The impact of collinearity between predictors will be assessed and the final model modified as necessary.

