9.5.6 Determine MIDs and Clinically-Meaningful MUI Definitions

We will explore potential MIDs for UDI total score and stress and irritative subscores for this MUI population. MIDs will be calculated using anchor- and distribution-based approaches. Potential anchors include global impression of change, incontinence episodes from the bladder diary, and request for additional treatment. The change from baseline UDI total score and stress and irritative subscores for each ESTEEM participant will be compared to the MIDs estimated from the ESTEEM data, and the percentage of participants who meet or exceed the MID will be compared between treatment groups..

We will attempt to create threshold definitions, based on baseline measures of the UDI, IIQ, OAB-q, UDE, and baseline bladder diary parameters in isolation and in combination, that are predictive of clinical success at 1 year. Definitions of success will be based on a change from baseline in total UDI score, UDI-irritative score or UDI-stress score at least as large as the MID for this MUI population.

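### Predictors of UDI change (SAP 9.5.3) and baseline UDI cut-offs for success (9.5.6) are coupled to the baseline score, and nothing guarantees adjustment for it

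*SAP*

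**What the plan says.** The third exploratory aim (Protocol 1.3) is worded "Predictors of poor outcomes: To develop models to identify predictors of change of MUI, OAB, and SUI outcomes". SAP 9.5.3, with the same text in Protocol 6.2.3.c, carries it out with regression models to "identify predictors of change from baseline to 1 year for UDI total score and stress and irritative subscale scores". The candidates are given as "Potential predictors will include age, diary parameters such as number of UUI episodes/3 days, functional bladder capacity, bother severity at baseline". Each is explored in "models that include one predictor plus stratification factors (center and baseline urge IE group"), and a predictive model is then built by backward selection with a check for collinearity. On who is analysed: "Participants who request additional treatment prior to 1 year will not be included in the predictive models".

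The sixth exploratory aim (SAP 9.5.6; Protocol 6.2.3.f) seeks threshold definitions "based on baseline measures of the UDI, IIQ, OAB-q, UDE, and baseline bladder diary parameters in isolation and in combination" that predict clinical success at 1 year. On success itself: "Definitions of success will be based on a change from baseline in total UDI score, UDI-irritative score or UDI-stress score", of at least the MID for this population.

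Neither section makes the baseline UDI score a required covariate or models the 12-month score. Protocol 3.4.1 argues for change scores, but only for comparing the randomised arms.

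**The concern.** Change is the 12-month score minus the baseline score, so baseline enters the outcome with a minus sign. A woman whose baseline is high, partly by chance, will tend to show a larger fall whatever her prognosis. Any predictor correlated with baseline UDI takes on part of that association unless baseline UDI is in the model.

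Randomisation makes this harmless when arms are compared, because they share a baseline distribution. It gives no protection when women of different severity are compared, which is what these two aims do.

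The third aim is labelled as being about poor outcomes. Protocol 2.9 asks which women with mixed incontinence should or should not have a sling, and Protocol 2.10 expects predictive information that can be applied directly in care. A table listing high baseline severity as a predictor of improvement could be read as a good prognosis, although those women may have more symptoms at 12 months.

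**Working it through.** **Plan's own figure.** The documents give none for these analyses. The nearest is the sample size: 200 / 0.85 = 235.3, rounded up to 236 per group, so 472, as stated. With 30% and 20% requesting additional treatment (SAP 6), about 200 x 0.7 + 200 x 0.8 = 300 women remain for the 9.5.3 models.

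**Inputs.**
- UDI-irritative SD 25.4 at baseline and 15.1 at 12 months, from the earlier trial of midurethral slings (Protocol 2.5).
- UDI-total at baseline 120 (SD 49), from the urge-predominant trial (Protocol 3.4.1).
- Planning SDs 25.6 (irritative) and 50.4 (total), from SAP 6. The SAP does not say what they are SDs of; I assume SDs of change.
- The baseline-to-12-month correlation r and the 12-month SD of UDI-total are not given. I derive or vary them.

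**Formulae.** With baseline SD s0, 12-month SD s1 and SD of change sd:
- r = (s0² + s1² - sd²) / (2 s0 s1)
- slope of the 12-month score on baseline = r s1/s0
- slope of change on baseline = r s1/s0 - 1
- corr(change, baseline) = (slope of change) x s0/sd

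**UDI-irritative.** r = (645.16 + 228.01 - 655.36) / 767.08 = 0.284. The slope is 0.284 x 15.1/25.4 = +0.17 on the 12-month score and 0.17 - 1 = -0.83 on change. With s1/s0 = 0.594, the two slopes have opposite signs for every r between 0 and 1. At r = 0.1 they are +0.06 and -0.94; at r = 0.9, +0.54 and -0.47.

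**UDI-total** (s0 = 49, sd = 50.4):

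| Assumed 12-month SD | r | Slope, 12-month score | Slope, change | corr(change, baseline) |
|---|---|---|---|---|
| 30 | 0.26 | +0.16 | -0.84 | -0.82 |
| 40 | 0.37 | +0.30 | -0.70 | -0.68 |
| 49 | 0.47 | +0.47 | -0.53 | -0.51 |

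If 50.4 is not the SD of change, then with equal SDs corr(change, baseline) = -√((1 - r)/2). At r = 0.7 that is -√0.15 = -0.39.

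**A marker with no prognostic value once baseline is known.** Suppose it correlates 0.4 with baseline UDI-total (assumed). Its correlation with change is 0.4 x corr(change, baseline): -0.33, -0.21 and -0.15 for -0.82, -0.51 and -0.39. With n = 300, t = ρ√298/√(1 - ρ²), about -6.0, -3.6 and -2.7. This leaves out the urge-episode group, which the plan does include and which would absorb part of it for a marker such as the urge episode count.

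**SAP 9.5.6, UDI-total with no mean change at all.** Take mean 120, SD 49 at both times and r = 0.471. Given a baseline one SD from the mean, expected change is ∓0.529 x 49 = ∓25.9, with residual SD 49 x √(1 - 0.471²) = 43.2.
- MID 35: success probability is Φ((25.9 - 35)/43.2) = 0.42 at one SD above and Φ((-25.9 - 35)/43.2) = 0.08 at one SD below.
- MID 11: 0.64 above and 0.20 below.
- Expected 12-month scores are 120 + 0.471 x 49 = 143 above and 97 below.

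The group with more successes finishes worse.

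**SAP 9.5.6, UDI-irritative with the sling trial's values.** I simulated 400,000 bivariate normal pairs (means 41.2 and 8.9, r = 0.284), clipped to 0-100. Entry was limited to scores of at least 11.1, the lowest eligible score: one of six items at 2 gives 2/6 x 100/3. Success at an illustrative MID of 15 was 55%, 91% and 99% by rising baseline tertile, while mean 12-month scores were 9.4, 11.8 and 15.2. A woman entering at 11.1 cannot fall by 15 even with complete resolution.

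**The case against.** The strongest reply is that backward selection largely repairs the final model. If baseline bother is baseline UDI, its association with change is strong enough that about 300 women would almost certainly keep it in. The other coefficients are then exactly those of a 12-month-score model adjusted for baseline. This stands. It does not cover the one-predictor models or the baseline coefficient itself, and nothing in the plan guarantees retention.

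Four stronger readings are tempting, and the documents do not support them.
- **That 9.5.3 names the UDI as its bother predictor.** It does not define bother severity. The UDI is the natural reading, since Protocol 2.2 describes it as measuring bother, but only 9.5.6 names it outright.
- **That the whole negative slope is regression to the mean.** The irritative SD fell from 25.4 to 15.1 in the sling trial, so part of it is real room to improve. Entry also selects on two UDI items, not on the total.
- **That modelling change is simply a mistake.** Protocol 2.10 asks who improves, worsens or stays the same, and expected change given baseline is a legitimate quantity.
- **That success will be judged at 35 or 15 points.** SAP 9.5.6 uses an MID estimated from this trial, which Protocol 6.1.1 says could be smaller. The published values here are illustrations; the null-case pattern persists at 11 points.

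**Conclusion.** The concern holds for the one-predictor models in 9.5.3, for the final model if baseline UDI is not retained, for the baseline severity coefficient in any of them, and explicitly for the baseline UDI cut-offs in 9.5.6.

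The sign reversal for UDI-irritative (-0.83 against +0.17) rests on the sling trial's SDs and on 25.6 being the SD of change; with those two SDs, the reversal itself holds for any positive r. For UDI-total the coupling is about -0.5 to -0.8 if 50.4 is the SD of change and the 12-month SD is 30 to 49. It is about -0.4 with equal SDs and r = 0.7.

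A reader might infer that the trial's main results are affected, or that every reported predictor will be spurious. Neither follows. Both aims are exploratory, all randomised comparisons are unaffected, and so are predictors unrelated to baseline UDI, such as age.

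**What to change.** **SAP 9.5.3.** Force the baseline score of the same UDI scale into every one-predictor model and the final model, exempt from backward selection. The outcome need not change. Writing change as F - B, a fit of F on B and X with coefficients b and c becomes a fit of change with coefficients b - 1 and c, so all other coefficients are identical. Do not interpret the baseline UDI coefficient on change as a predictor of good or poor outcome; report its association with the 12-month score. State which measure bother severity refers to.

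**SAP 9.5.6.** Keep the MID-based definition of success if wanted, but do not evaluate baseline UDI cut-offs against UDI change alone. Report the thresholds also against a 12-month state that SAP 9.2 already defines, for example PGI-S normal or mild.

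**Cost.** A wording change and a little more analysis, on data already collected. Some associations will look weaker than under the present text.

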Although routine educational pamphlets may be provided to subjects prior to their enrollment into ESTEEM per usual care at each site, once enrolled, no additional educational pamphlets may be provided to either control or intervention subjects outside of the protocol. The control group will complete bladder diaries and undergo PFM assessments at the same time intervals as the intervention group to control for any potential independent effects that bladder diary completion may have.

Rationale for including women who have previously tried behavioral and/or physical therapy:

There are many reasons to include women who have previously tried behavioral and/or pelvic floor physical therapy. First, women eligible for ESTEEM must have at least moderately bothersome MUI and desire surgery; therefore, even though these women have had treatments in the past, they did not improve enough to forego additional treatment. In addition, ESTEEM is evaluating the effect of **combined surgical and BPTx treatment and not just BPTx alone**. Therefore, women who have previously failed BPTx alone in the past may still significantly improve with combined surgical/BPTx treatment or surgery alone and there is no evidence to support their exclusion from this trial. *This is the most important reason why these women should be included.* Second, many women who have previously tried behavioral and/or physical therapy may have had a wide range of non-standardized interventions to varying degrees, durations, and with various components. Therefore, it is difficult to conclude that they may be at “higher risk” for failure, or that they will not benefit from the ESTEEM intervention. In ESTEEM, the BPTx protocol is based on existing evidence for specific BPTx components and the expertise of interventionists focused solely on improving MUI symptoms. This standardized protocol can potentially enhance the surgical effects for women with MUI. The protocol does provide the opportunity to identify risk factors for failure of a standardized BPTx intervention which will help build additional evidence for future trials.

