Although our primary outcome is at 12 months, the team was interested in whether perioperative BPTx may be associated with a delayed *time to failure* compared to Control. In other words, is BPTx associated with a significant effect, but the effect is not sustained at the 12 month time point? For example, if BPTx could delay the need for anti-muscarinics for up to 9 months, this would be relevant information for counseling women and perhaps clinically recommending perioperative BPTx. As described previously, failure will be defined as initiation of any additional treatment for either SUI or UUI/OAB symptoms.

A class of survival model which can account for interval censoring (outcomes measured at pre-planned time points as opposed to continuously over time) will be used to determine if combined MUS+BPTx is associated with a decrease time to failure compared to MUS alone between 3-12 months. Depending on the distribution of the observed data, an accelerated failure time frailty model or a Bayesian survival model may be used. The model will be adjusted for the design effects of stratification by center and by baseline urge IE group.

c. Predictors of treatment success and failure

Regression models will be created to identify predictors of change from baseline to 1 year for UDI total score and stress and irritative subscale scores. Participants who request additional treatment prior to 1 year will not be included in the predictive models. Potential predictors will include age, diary parameters such as number of UUI episodes/3 days, functional bladder capacity, bother severity at baseline. The relationship between potential predictors and outcomes will be explored in models that include one predictor plus stratification factors (center and baseline urge IE group). Predictive models will be constructed using backward selection of predictors. The impact of collinearity between predictors will be assessed and the final model modified as necessary.

d. Quality of life/global impression

For these scales and associated subscales, differences from baseline will be calculated and methods described for analysis of the primary outcome will be used to test for differences between treatment groups from baseline and 6 and 12 months.

e. To describe safety and initiation of additional treatment for worsening OAB and/or persistent SUI

We will describe rates of sling revision due to worsening OAB symptoms and rates of additional treatment.

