7.8 Examination of Subgroups

No subgroup analyses are planned.

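### The one-predictor models in SAP 9.5.3 omit treatment arm and fit the UUI-episode count beside a stratum that is the same count cut at 4

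*SAP*

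**What the plan says.** SAP 9.5.3 names the candidates: "Potential predictors will include age, diary parameters such as number of UUI episodes/3 days, functional bladder capacity, bother severity at baseline". It explores each in "models that include one predictor plus stratification factors (center and baseline urge IE group". Protocol 6.2.3, item c, says the same: "The relationship between potential predictors and outcomes will be explored in models that include one predictor plus stratification factors". Neither text lists randomized arm as a term or as a candidate, and neither makes an exception when the predictor is the UUI count.

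The multivariable step is brief: "Predictive models will be constructed using backward selection of predictors", then "The impact of collinearity between predictors will be assessed and the final model modified as necessary". It does not say whether arm or the strata stay in. The analysis set is restricted: "Participants who request additional treatment prior to 1 year will not be included in the predictive models".

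Four other places bear on the point.

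- Protocol 3.3 and SAP 4.3 define the urge-IE stratum as 4 or more urge episodes on the 3-day diary. Protocol 4.2 requires at least 1 for entry.
- Protocol 5.3, explaining why women with prior therapy are admitted, says: "The protocol does provide the opportunity to identify risk factors for failure of a standardized BPTx intervention".
- SAP 7.8 says: "No subgroup analyses are planned".
- Protocol 6.2.3, item g, and SAP 9.5.7 plan separate work on unsuccessful muscle strengthening and urge suppression and how these affect urinary outcomes. The protocol places it in women randomized to BPTx.

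**The concern.** Two features of the stated model limit what it can show.

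First, a pooled slope averages the two arms. A baseline factor that predicts poor change after a sling in everyone, and one that matters only under BPTx, both appear as a single main effect. The second appears at about half its size. Protocol 5.3 mentions risk factors for failure of BPTx, and the stratification rationale in Protocol 3.3 rests on a study of failure of behavioral treatment, so the distinction is of interest to this trial.

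Second, fitting a count next to its own dichotomy leaves only the variation within the two strata to estimate the count's slope. The question becomes whether more episodes matter among women already on the same side of 4, which is narrower than whether UUI frequency predicts outcome.

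Excluding women who request additional treatment adds a smaller issue. It selects on a post-randomization event that the plan expects to differ by arm. In the retained set, randomization no longer guarantees balance of baseline predictors across arms, so omitting arm could shift a slope as well as add noise.

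**Working it through.** **Plan's own figure.** 200 per group with 15% dropout (SAP 6.3): 200/0.85 = 235.3, rounded up to 236; 2 x 236 = 472, as stated. SAP 9.5.3 gives no n or power of its own.

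**Size of the predictor set.** Using 200 per group after dropout and additional-treatment rates of 20% and 30% (SAP 6): 200 x 0.80 = 160 BPTx, 200 x 0.70 = 140 control, 300 in all. BPTx share p = 160/300 = 0.533.

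**Omitting the arm main effect.** Added residual variance as a share of SD² is p(1-p)d²/SD², with SD 50.4 (SAP 6.1) and p(1-p) = 0.249.

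- d = 19: 0.249 x 361/2540 = 3.5%; SE factor √1.035, or +1.8%.
- d = 35: 0.249 x 1225/2540 = 12.0%; SE factor √1.120, or +5.8%.

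This assumes arm is unrelated to the predictor. The documents give no basis for sizing any bias from the exclusion of women who request additional treatment.

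**Pooling a BPTx-only slope.** Assume a slope b per predictor SD under BPTx, none in control, residual SD 50.4 and a normal approximation. The pooled slope is p x b. Standard errors are:

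- pooled: 50.4/√300 = 2.91
- BPTx-only fit: 50.4/√160 = 3.98
- interaction: 50.4 x √(1/160 + 1/140) = 5.83

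| b (UDI points per SD) | Pooled slope | Power, pooled | Power, BPTx-only fit | Power, interaction |
|---|---|---|---|---|
| 8 | 4.3 | 31% | 52% | 28% |
| 10 | 5.3 | 45% | 71% | 40% |
| 12 | 6.4 | 59% | 85% | 54% |

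For slopes of +10 and -10 in the two arms, the pooled slope is (0.533 - 0.467) x 10 = 0.7 with 6% power; the interaction test has 93%.

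**Count beside its own cut.** Variance inflation is 1/(1 - r²), where r is the correlation of the count with the indicator for 4 or more. The count distribution is not in the documents. The values below simulate counts truncated at 1 or more; the mean is that before truncation. The last column takes a linear effect that would have 80% power with the count alone and divides its test statistic by the square root of the inflation.

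| Assumed counts | r² | Variance inflation | 80% power becomes |
|---|---|---|---|
| Poisson, mean 3 | 0.68 | 3.1 | 35% |
| Negative binomial, mean 3, size 1 / 2 | 0.54 / 0.61 | 2.2 / 2.6 | 47% / 42% |
| Poisson, mean 5 | 0.50 | 2.0 | 51% |
| Negative binomial, mean 5, size 1 / 2 | 0.41 / 0.46 | 1.7 / 1.9 | 57% / 54% |
| Poisson, mean 8 | 0.16 | 1.2 | 73% |
| Negative binomial, mean 8, size 1 / 2 | 0.29 / 0.30 | 1.4 / 1.4 | 65% / 65% |
| Poisson, mean 12 | 0.02 | 1.0 | 79% |
| Negative binomial, mean 12, size 1 / 2 | 0.21 / 0.19 | 1.3 / 1.2 | 70% / 71% |

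The loss is largest when the cut falls near the middle of the distribution and nearly vanishes when almost every woman is above it.

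**The case against.** The best defense is that the model fits its aim. Aim 3 (SAP 3.1.3) asks for predictors of UDI change overall, every woman is to receive a sling, and a pooled prognostic model answers that. Adjusting for stratification factors is also the trial's general practice. This stands, and it keeps the point small. SAP 7.6, however, requires the strata only in primary and secondary models, so nothing prevents the count from replacing the stratum here.

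Several stronger readings are tempting, and the documents do not support them.

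- *The trial cannot find risk factors for BPTx failure.* A pooled model dilutes a BPTx-only slope but does not hide it. Protocol 6.2.3, item g, and SAP 9.5.7 cover part of the question, through failed strengthening and urge suppression rather than UDI change by arm.
- *SAP 7.8 closes off any other look.* It says only that none is planned; SAP 2 allows further exploratory analyses without an update.
- *Protocol 5.3 commits the trial to this analysis.* It speaks of an opportunity, within an eligibility rationale, and specifies no analysis.
- *UUI severity will be screened out.* No rule makes entry to the multivariable model depend on the one-predictor result. The stratum is itself a severity term, and the cited evidence in Protocol 3.3 is a threshold. The collinearity provision also allows the final model to be changed, although it does not reach the one-predictor models.
- *UUI count is the chief predictor.* SAP 9.5.3 ranks none, and Protocol 3.3 calls severity a potential risk factor.

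Interactions for every candidate would add many weak tests, so that extension is not requested.

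**Conclusion.** The point holds as a modest improvement to a stated exploratory method. The model terms are written out, and they omit arm and pair the UUI count with its own cut.

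Leaving out the arm main effect costs about 2-6% in standard error for differences of 19-35 points. The larger limitation is interpretive: general and BPTx-specific predictors are not separated, and a BPTx-only slope is reduced to about 53% of its size on the planning figures. Keeping the stratum inflates the count's variance roughly 1.2-3 times for assumed means of 3-8, and about 1.0-1.3 times at a mean of 12.

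These sizes rest on the planning rates of additional treatment and SD 50.4, on assumed count distributions, and on illustrative slopes of 8-12 points per SD. No primary or secondary result, and no sample size, is affected.

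**What to change.** In SAP 9.5.3:

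1. Include treatment arm in every predictor model.
2. When the number of UUI episodes is the predictor, use the count in place of the urge-IE stratum. The other one-predictor models still carry the stratum, so a threshold effect remains visible.
3. State whether arm and the strata are kept through backward selection.
4. Optionally, report one arm-by-urge-IE-severity interaction, labeled exploratory and read as low-powered (28-54% in the BPTx-only examples above).

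The cost is a few sentences and one or two model terms. No new data are needed.

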2.10. Innovation

[figure not shown]
This proposal is innovative for several reasons. First, it studies a population of women who are often excluded from clinical intervention trials but are at high risk for failing segregated SUI and UUI treatments. Second, in contrast to the historical paradigm of initiating treatments separately and stepwise for SUI and UUI, we will evaluate the effect of a combined surgical and non-surgical approach to optimize treatment outcomes. Third, this study will provide critical information regarding OAB outcomes after MUS and will be

powered to allow reporting of OAB and SUI outcomes separately after treatment. Finally, we will gain important predictive information regarding which patients may experience improvement, worsening, or no change in their OAB symptoms. At the completion of this study, we will understand whether a combined behavioral/surgical treatment approach is superior to surgery alone and will have predictive information that will be directly applicable to the clinical care of patients with this challenging condition.

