The team discussed the issue of whether bladder capacity should determine eligibility. Historically, some clinicians have used bladder capacity as a criteria for whether a woman with MUI is eligible for an anti-incontinence procedure for SUI, often excluding women with capacities <150-200 cc to avoid exacerbation of OAB symptoms. Upon review of the literature, there is very little evidence to support excluding women with a "small" bladder capacity, or to guide what volume defines a "small" capacity bladder. Gamble et al performed a retrospective study to evaluate predictors of persistent postoperative detrusor overactivity after a variety of slings.⁷⁹ They found that the mean maximum cystometric capacity was smaller in women with postoperative persistent DO compared to those with resolved DO. However, the mean capacity in women with persistent DO was 459 cc (SD 185) versus 539 cc (SD 176), which does not support the traditional teaching of avoiding slings in women with capacities less than 150-200 cc. Also, 37% of their study population included traditional bladder neck slings, which may be more obstructive than MUS. Finally, the proportion of women reporting UUI *symptoms* in this study was not different between women who had resolved versus persistent DO, highlighting the limitation of using UDE parameters to predict symptoms. Numerous other studies have failed to demonstrate any specific bladder capacity cutoff that is associated with better or worse outcomes or poses a safety issue for MUS.

Because there is a lack of evidence to support setting a minimum bladder capacity cutoff for this study, women determined to be eligible for a MUS based on their clinician's judgment will be eligible for ESTEEM, regardless of bladder capacity. One advantage of the ESTEEM design is that only women who have been offered a MUS by their clinician will be eligible. Therefore, if the provider determines that the patient is not clinically a candidate for a MUS, she will not be eligible. In addition, we will be excluding women with a history of painful bladder or chronic pelvic pain syndromes who often have "small" capacity bladders. To further contribute to the literature about this issue, we will collect data on both maximum cystometric capacity on UDE and functional bladder capacity based on voiding diaries and evaluate these variables as potential predictors of worsening OAB symptoms in our exploratory analyses.

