6 SAMPLE SIZE DETERMINATION

This study is designed to compare the relative effectiveness of MUS and MUS combined with BPTx. Power and sample size calculations were generated to determine the sample size needed to test for treatment difference favoring MUS combined with BPTx across the study arms for a variety of assumptions about effective size and follow-up time. Sample size estimates are based on simulations using analysis methods accounting for both the rate of additional treatment in the two groups as well as UDI total score or subscore values over the 12 month follow up. We assumed that 30% of women in the MUS only group and 20% of women in the MUS+BPTx group would request additional treatment. In TOMUS, 10-12% of women who had baseline MUI had persistent UUI postoperatively based on MESA responses and/or initiation of anticholinergic treatment.²⁴ In Barber's TVT vs TOT equivalence trial, 70% reported baseline MUI and postoperatively, 30% of all women reported bothersome UUI with 16% of subjects on anticholinergic treatment postoperatively.³¹ In Abdel-Fattah's transobturator MUS trial, 25% reported worsening OAB and almost all of these women were on anticholinergic treatment postoperatively.³⁴ In Palva's TVT vs TVT-O trial, 174 women reported preoperative UUI and of these, 7 women (4%) had tried anticholinergics postoperatively after 3 years. Therefore, based on existing MUS trials, the rate of additional treatment for OAB ranges from 4-25%, supporting our conservative assumption that 30% of women will request additional treatment in the MUS only group.

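### The exploratory predictor models use backward selection with no correction for it, so their fit and coefficients will on average look too good

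*SAP*

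**What the plan says.** SAP 9.5.3, which repeats protocol 6.2.3.c, models three outcomes, namely "predictors of change from baseline to 1 year for UDI total score and stress and irritative subscale scores". Each candidate is first examined alone with the stratification factors. Then "Predictive models will be constructed using backward selection of predictors". A further data-dependent step follows: "The impact of collinearity between predictors will be assessed and the final model modified as necessary".

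The candidates are given by example: "Potential predictors will include age, diary parameters such as number of UUI episodes/3 days, functional bladder capacity, bother severity at baseline". Other sections add to them. On cystometric and functional bladder capacity, protocol 4.3 says the team will "evaluate these variables as potential predictors of worsening OAB symptoms in our exploratory analyses". Protocol 3.3 keeps preoperative detrusor overactivity for exploratory work, and protocol 5.5.1 collects urodynamic variables because they might predict outcome. Neither document gives a total number of candidates or a threshold for keeping one.

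The models leave out some women: "Participants who request additional treatment prior to 1 year will not be included in the predictive models".

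Neither document plans cross-validation, bootstrap validation, shrinkage or optimism correction for these models. The only bootstrap is for the interval of the cost-effectiveness ratio (protocol 6.2.3.h). The work is exploratory aim 3, but protocol 2.10 says that at the end of the study the team "will have predictive information that will be directly applicable to the clinical care of patients".

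**The concern.** Backward selection keeps the predictors that look strongest in the sample at hand, and the same sample then estimates their effects. Three consequences are well known. R² measured on those women exceeds what new women would show. A true predictor is more likely to be kept when its estimate happens to be large, so kept coefficients are too big on average. Ordinary standard errors ignore the search, so intervals can be too narrow and some kept terms can be noise. The last two depend strongly on how many candidates enter and how they are removed, and the plan fixes neither.

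At stake is the counselling use foreseen in the protocol. A surgeon could be given a model that seems to explain more than it does, or a predictor that later data do not confirm.

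**Working it through.** **The plan's own figures.** The predictor analysis states none to reproduce. The sample size reproduces: 200 / 0.85 = 235.3, rounded up to 236 per group, and 2 × 236 = 472.

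**Usable number of women.** From SAP 6: "We assumed that 30% of women in the MUS only group and 20% of women in the MUS+BPTx group would request additional treatment". The mean is (30% + 20%) / 2 = 25%. With 15% dropout, independent of additional treatment, n ≈ 472 × 0.85 × 0.75 = 301. If nobody requested additional treatment, n ≈ 472 × 0.85 = 401.

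**Simulation inputs, all assumed except n.**
- Linear model with n = 300, eight site indicators and the urge-episode group always kept.
- Candidates correlated 0.2 pairwise; 5, 10, 20 or 30 of them.
- Four true predictors of equal size, scaled so that β′Cβ = R²/(1 − R²), with C the candidates' correlation matrix, residual variance 1 and R² = 0.15.
- The least significant candidate is removed until all have p ≤ 0.05.
- 80 to 600 simulated trials per setting.

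**Main results.** R² here is for the predictor part, with the stratification terms set aside.

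| Candidates | Apparent R² | R² in new women | Gap | Any noise predictor kept | Coverage of nominal 95% intervals, kept terms |
|---|---|---|---|---|---|
| 5 | 0.158 | 0.122 | 0.036 | 7% | 96% |
| 10 | 0.163 | 0.118 | 0.045 | 32% | 91% |
| 20 | 0.169 | 0.111 | 0.058 | 56% | 83% |
| 30 | 0.180 | 0.096 | 0.084 | 82% | 71% |

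True predictors that were kept had coefficients averaging 1.18 to 1.20 times their true value.

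**Sensitivity** (5, 10, 20 and 30 candidates in order).
- Any noise predictor across all three outcome models, residual correlation 0.7 (assumed): 15%, 58%, 89%, 95%.
- Removal at p > 0.10 instead, one model: 12%, 49%, 86%, 95%.
- No true predictors at all, removal at 0.05: at least one kept in 19%, 36%, 66%, 83%.
- n = 400: apparent v new-data R² 0.155 v 0.133, 0.157 v 0.130, 0.165 v 0.124, 0.173 v 0.116; coefficients inflated by about 9–10%.

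A separate simulation with other assumed inputs (340 women, five true predictors, true R² 0.10, 15–25 candidates, removal at 0.05 or 0.10) gave apparent R² 0.11–0.13 against 0.05–0.06 in new women, coverage 75–87% and coefficient inflation 9–16%. The direction is the same; the size moves with the inputs.

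**Does the remedy work?** Corrected R² = apparent R² − mean over resamples of (R² in the resample − R² of that resample's model in the original data), with the selection repeated in every resample. With n = 300 and 60 resamples, for the full model including stratification terms:

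| Candidates | Apparent | Corrected | R² in new women |
|---|---|---|---|
| 10 | 0.188 | 0.093 | 0.087 |
| 20 | 0.191 | 0.062 | 0.078 |
| 30 | 0.202 | 0.038 | 0.071 |

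The correction removes the optimism, and goes too far with 20 or more candidates.

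**The case against.** The analysis is openly exploratory and does not touch any treatment comparison. SAP 2 lets exploratory analyses be added without an update, so a bootstrap could be run anyway. The claim about clinical care is one forward-looking sentence in the protocol's Innovation section and is not repeated in the SAP. The documents name only a handful of candidates, and with five the harm is small: 7% of models keep a noise term and intervals cover 96%. All of this stands, and it limits the importance of the point. It does not remove it: being allowed to validate is not a plan to do so, the list is open-ended, and fit and coefficients were inflated even with five candidates.

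A reader might infer three stronger things that the documents do not support.
- That the trial is bound to name chance predictors with intervals that are too narrow. That depends on a candidate count and a removal rule that are not stated.
- That the final model will be presented as though fixed in advance. Neither document says how these results will be reported. SAP 9.5.3 is open about modifying the model, and the display list in SAP 15 names no predictor table, though displays may be added.
- That the models will overstate prediction of who fails after a sling. Protocol 3.4.1.c counts a request for additional treatment as failure, and those women are left out. The models describe UDI change in the rest.

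**Conclusion.** The concern holds as a cheap improvement of low severity. Uncorrected backward selection will on average overstate fit and the size of kept coefficients. That direction held at every candidate count tried, at n = 300 and at n = 400. Under the main assumptions the apparent R² is too high by 0.036 to 0.084. Noise predictors and under-covering intervals become likely from about 10 candidates upward, but are not certain.

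The sizes rest on assumed numbers of candidates and true predictors, true R², correlation and removal threshold. SAP 13 reports relatively few women meeting the failure criteria, so the usable number may lie nearer 400 than 300. That would shrink the optimism, not remove it.

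**What to change.** In SAP 9.5.3:
1. List the candidate predictors, the retention rule and the rule for handling collinearity before unmasking, or, if that point has passed, before these models are fitted.
2. Repeat the whole selection process, including the collinearity rule, in each of, say, 500 bootstrap resamples.
3. Report optimism-corrected R², the calibration slope, how often each predictor is selected, and coefficients shrunk by that slope.
4. State that the intervals and p-values of the selected model are not adjusted for selection, or take intervals from the full pre-listed model. The bootstrap in step 2 does not by itself repair them.
5. Describe the results as hypothesis-generating, and temper the sentence in protocol 2.10 to match.

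The cost is some SAP wording and a modest amount of programming, with no new data. Reported performance will be lower, and with many candidates the correction can be too pessimistic, which is a further reason to keep the list short.
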